3.3.4.3. MANAGEMENT OF OVERDOSE

The intended dose of ALX-0171 should not be exceeded during the study. No antidote is available.

Overdoses that occur during the study should be documented and reported to the Sponsor or designee whether or not it results in an AE/SAE. Overdoses with signs and symptoms need to be reported as an AE/SAE. For information on medication errors, please refer to section [4.2.1](#).

3.3.5. DRUG ACCOUNTABILITY

The Pharmacist, the Investigator or his/her designee is responsible for the acknowledgement of receipt for each shipment of study drug/inhalation system and will verify the condition and quantity of the study drug and other clinical supplies related to Investigational Medicinal Product (IMP) administration.

At study site, the study drug will be kept in a locked and secured storage facility accessible only to those authorized by the Investigator to dispense the study drug.

The responsible person will keep an inventory. This will include the quantity of study drug/inhalation system received for the study and a record of the materials that are dispensed, to whom (subject number) and when.

The pharmacist, the Investigator and/or designated personnel will conduct a final inventory of the study drug/inhalation system and will record the results of this inventory. Upon Sponsor approval, all study drug and clinical supplies will be returned to the depot, or will be destroyed locally according to local regulations and site procedures.

Instructions for drug/inhalation system accountability are available in the manual concerning study drug.

3.3.6. STUDY DRUG HANDLING

Instructions for study drug receipt, handling, storage and administration are available in the manuals concerning study drug and IWRS/IVRS.

Packaging and Labeling

Final packaging and labeling will comply with the local regulatory requirements. Details on packaging and labeling are provided in the study drug manual.

Storage

Study drug will be provided under refrigerated conditions and must be stored in a secure, limited-access location protected from light and under the storage conditions specified by the Sponsor.

Study drug must be refrigerated at 2°C to 8°C and should be stored in the secondary packaging until administration. It should not be frozen or shaken.

Site storage conditions should be monitored by the site personnel and reviewed by the monitor during site visits. Deviations from the storage requirements must be documented and reported to the Sponsor, according to the instructions provided in the manual concerning study drug.

Dispensing

The Investigator or qualified designee(s) will dispense (via IWRS/IVRS) study drug/inhalation system to subjects who have met the entry criteria. Clinical supplies (including study drug) may not be used for any purpose other than that which is stated in this protocol.

Product Quality Complaint

Product quality complaints have to be communicated (written or electronically) to the Sponsor. Instructions for product quality complaint handling are available in the manual concerning study drug.

For medical device issues see section [4.2.2](#).

3.3.7. CONCOMITANT THERAPY

Any concomitant medication (including over-the-counter medications and herbal supplements) taken during the study (i.e., from signing of the ICF until the subject's last visit), must be recorded in the eCRF. Items to be recorded concerning concomitant medication include: dose and units of dose, start and end date, administration frequency, route of administration, therapeutic indication, brand name (or generic name if brand name is not available). Of note, previous medications relevant for eligibility will also be recorded in the eCRF.

3.3.7.1. STANDARD OF CARE TREATMENT

The treatment and care provided to each subject are determined by the Investigator (or designee) according to institutional practice. The recommendations on the diagnosis, management, and prevention of bronchiolitis, as described by the American Academy of Pediatrics [1], may be followed in addition to institutional practice.

Treatment may include (but is not limited to) the following:

- Oxygen supplementation through nasal cannula, via face mask or headbox. The initiation, monitoring and weaning of oxygen supplementation will follow local practice. It should be removed for the nebulized study drug administration, during which air or oxygen flow of 2 L/minute is provided
- Fluid/food supplementation (i.v. or via nasogastric tube, if applicable)
- Antipyretics and/or nonsteroidal anti-inflammatory medication
- Inhalation of hypertonic saline (but not within 4 hours before start or 4 hours after the EOS drug administration)
- Short acting β_2 -agonists
- Antibiotics (in case of secondary bacterial infection)
- Epinephrine
- Anticholinergics

Apart from those listed under the prohibited medications (see below), concomitant medications are permitted at the Investigator's discretion (based on medical need).

3.3.7.2. PROHIBITED MEDICATIONS

The following medications are prohibited up to the FU visit (Day 14 ± 2 days):

- Ribavirin, i.v. immunoglobulin and palivizumab Heliox
- Leukotriene receptor antagonists (LTRAs, i.e. montelukast) and/or sodium cromoglycate; initiation of LTRAs and/or sodium cromoglycate is not permitted; infants who are on a maintenance therapy at screening are to continue their usual dose during the study.

- Exogenous surfactant
- Systemic corticosteroids; initiation of inhaled corticosteroids is not permitted; infants who are on a maintenance therapy of inhaled corticosteroids at screening are to continue their usual dose during the study. Of note, topical corticosteroids for the treatment of skin disorders are permitted.
- Mucolytics are permitted until screening but their continuation or initiation during the study is not allowed.

Subjects whose respiratory condition is deteriorating (e.g., hypercapnia with $pCO_2 > 8 \text{ kPa}/60 \text{ mmHg}$, decreased consciousness) and need to start non-invasive respiratory support or invasive ventilation need to discontinue study drug treatment but should remain in the study according to the in-hospital post-treatment period as specified in the [Schedule of Assessments](#), and should also attend the FU and EOS visits.

Subjects on HFOT as standard of care at inclusion and for whom the flow needs to be increased to levels not enabling study drug nebulization and/or above 2 L/kg/minute also need to discontinue study drug treatment and be further followed up as described above. SAE reporting is required for these subjects with deterioration of the respiratory condition requiring above mentioned methods of ventilation.

After the end of the subject's participation in the study, each subject is to be treated according to standard clinical practice.

3.3.8. TREATMENT COMPLIANCE

Study drug will be administered by a health care professional in hospital, ensuring treatment compliance.

The exact times of study drug administration (i.e., initiation and end of each nebulization and number of interruptions, if any) will be recorded in the eCRF. In addition, acceptability of the face mask and the nebulizer after each complete or partial administration, and whether or not correct and complete administration could be achieved will be documented in the eCRF. Compliance will be further confirmed by bioanalytical assessment of ALX-0171 in blood samples, and could be further confirmed by electronic documentation of the administration on the nebulizer base unit.

3.4. WITHDRAWAL AND DISCONTINUATION CRITERIA

3.4.1. WITHDRAWAL FROM THE STUDY

Every reasonable attempt should be made by the Investigator (or his/her designee) to keep subjects in the study, however, a subject must be withdrawn from the study if:

- Study drug administration cannot be successfully initiated on Day 1 (see section 3.3.4.2).
- The Investigator considers it, for safety reasons, in the best interest of the subject.
- The parent(s)/legal guardian(s) withdraw(s) consent.

A subject may be withdrawn from the study if the subject and/or parent(s)/legal guardian(s) fail to comply with dosing, evaluations, or other requirements of the study.

In case a subject is withdrawn from the study for any reason other than death, lost to follow-up or informed consent withdrawal (including subjects randomized but not dosed), a Withdrawal visit should be conducted at the time of withdrawal.

The reason for withdrawal should be recorded in the eCRF. Investigators (or their designees) must attempt to contact the parent(s) or legal guardian(s) of subjects who fail to attend scheduled visits by telephone or other means, to exclude the possibility of an AE being the cause of withdrawal. Should this be the cause, the AE must be documented, reported, and followed-up as described in section 4.

If a subject is withdrawn from the study, the study monitor and the Sponsor are to be informed immediately.

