3.4.2. DISCONTINUATION OF STUDY DRUG

A subject must be discontinued from study drug treatment if:

- The randomization code is broken prematurely by the Investigator or Sub-Investigator.
- A severe and/or serious hypersensitivity reaction to study drug occurs.
- A severe and/or serious acute respiratory distress reaction induced by study drug administration occurs.
- The subject needs to start treatment with one of the medications listed as prohibited (see section 3.3.7).
- The subject needs to start non-invasive respiratory support, invasive ventilation or HFOT at levels not enabling removal of the cannula for administration of the study drug nebulization and/or levels exceeding 2 L/kg/min. The event will be captured as an SAE and will be monitored until resolution, as described in section 4.1.4.

- If the Investigator or the Sponsor / medical monitor deems it is in the subject's best interest.
- If on Day 2 or Day 3, study drug initiation*** has not been successful after 60 minutes, study drug treatment should be discontinued (i.e., in case dose initiation was not successful on Day 2, then no dosing on Day 3 should be done).

A subject may be discontinued from study drug treatment if an SAE occurs (if considered necessary or appropriate by the Investigator).

For subjects remaining hospitalized after study drug treatment discontinuation, in-hospital post-treatment assessments will be performed in addition as specified in the [Schedule of Assessments](#). Subjects who discontinued treatment prematurely (for any reason) should also attend the FU and EOS visits.

If a subject is discontinued from the study drug, the study monitor and the Sponsor are to be informed immediately.

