3.6.1.6. WITHDRAWAL VISIT

In case a subject is withdrawn from the study for any reason other than death, lost to follow-up or informed consent withdrawal (including subjects randomized but not dosed), a Withdrawal visit should be conducted at the time of withdrawal. The reason for withdrawal should be recorded in the eCRF.

If the Withdrawal visit assessments are performed within 6 hours after the Day 1, Day 2, Day 3, or in-hospital post-treatment day assessments have been performed, the assessments already done at the prior time point do not need to be repeated and only the additional assessments to be performed on the Withdrawal visit will need to be performed. No EOS visit needs to be performed after the Withdrawal visit.

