3.6.1.7. FOLLOW-UP AND END-OF-STUDY VISITS

Subjects who have received at least one dose of study medication should complete a FU visit on Day 14 (± 2 days), and an EOS visit on Day 28 (± 2 days). After the end of the subject's participation in the study, each subject is to be treated according to standard clinical practice.

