4.1.2. RECORDING OF ADVERSE EVENTS

What will be collected	All AEs
Responsibility	Investigator's responsibility
Period of collection AEs	All AEs will be reported from the time a signed and dated ICF is obtained until completion of the subject's last visit.
How are AEs elicited	
Spontaneous, unsolicited reports:
 
 - by subject, parents/caregivers and/or healthcare staff, - by observation (by the Investigator and/or healthcare staff), - by routine open questioning of the subjects (or parents/caregivers) or by the Investigator (e.g., "Is there anything new that you wish to discuss?") - by reviewing the diary with the subject's parent(s)/caregiver(s).

Where are AEs recorded	Documented in the source documents and the eCRF
When are AEs recorded	Detailed guidance on when to complete AEs is given in the CRF completion guidelines document.

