4.1.4. RECORDING OF SAEs

Collection and recording of SAEs by the Investigator	
What will be collected	All SAEs
Period of collection	
 From signed informed consent to subject's last visit: All SAEs. At any time after the subject's last visit: Only SARs. 
SAEs assessed by the Investigator as causally related to study drug will be notified to the Sponsor even after the subject's completion of his/her participation in the Clinical Trial (e.g., delayed onset/long latency SAEs).

Exemptions from SAE process below	None
Where are SAEs recorded	In addition to the recording of the AE as described in the section above, Serious AE specific information will also be recorded on the SAE form.
When are SAEs recorded	Within 24 hrs of Investigator/site's first knowledge (see also section 4.1.5)
How are SAEs recorded	
Indicate whether the report is initial or follow-up.
 
Attach supporting documents relevant to the SAE (e.g., hospital reports). The subject's name should be edited-out from any supporting documents.
 
Whenever possible, the overall diagnosis or overall syndrome's name should be used as the SAE verbatim. If the diagnosis is not available, use signs and symptoms and provide the final diagnoses as follow-up information when available. The AE verbatim term and the SAE verbatim term should match and must be clinically equivalent.
 
Include medical history and concurrent diseases that are relevant to the SAE.
 
The SAE must include the Investigator's assessment of the relationship of the event to study drug.
 
SAE forms must be signed by the Investigator or delegated person.

Causal relationship scale	
The assessment of the causal relationship between an SAE and the administration of study drug is a clinical decision based on all available information at the time of the completion of the SAE form.
 
The assessment is based on the question of whether there was a "reasonable causal relationship" to the study drug.
 
The following considerations should be taken into account for this assessment:
 
 Is the Time-to-Onset of the event compatible with a causal relationship? Was it "treatment-emergent"? Is it of common occurrence in the population under study?

Collection and recording of SAEs by the Investigator

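### Sections 3.4.1 and 3.4.2 give overlapping best-interest triggers with different follow-up, and withdrawing a dosed child for safety ends collection of new non-serious AEs and new unrelated SAEs

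*Protocol*

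**What the plan says.** Protocol section 3.4.1 opens with retention: "Every reasonable attempt should be made by the Investigator (or his/her designee) to keep subjects in the study". It continues "however, a subject must be withdrawn from the study if" and lists three conditions, one of which is "The Investigator considers it, for safety reasons, in the best interest of the subject". A child withdrawn this way has a Withdrawal visit at that time. Section 3.6.1.6 then states "No EOS visit needs to be performed after the Withdrawal visit", and footnote e of the Schedule of Assessments repeats it.

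Section 3.4.2 lists the conditions under which study drug must stop while the child stays in the study. One is "If the Investigator or the Sponsor / medical monitor deems it is in the subject's best interest". Children who stop drug for any reason are asked to attend the Day 14 and Day 28 visits.

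Section 3.6.1.7 states "Subjects who have received at least one dose of study medication should complete a FU visit on Day 14 (± 2 days" and goes on to require the Day 28 visit as well. It makes no exception for children withdrawn from the study.

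On event collection, section 4.1.2 states "All AEs will be reported from the time a signed and dated ICF is obtained until completion of the subject's last visit". For serious events, section 4.1.4 states "At any time after the subject's last visit: Only SARs".

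**The concern.** A site that thinks a dosed child's safety calls for a change can reach either section by much the same judgement. The choice decides whether the child is observed for new events to Day 28 or only to the day of withdrawal. Nothing in the protocol says how to choose.

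Safety and tolerability come first among the objectives, and section 1.3.3 names delayed adverse drug reactions as a potential risk. If follow-up is cut short for a safety reason, the missing observation is related to the outcome being measured. The SAP does not adjust for this. TEAE percentages use the whole Safety Population as denominator (SAP 6.1) and nothing is imputed (SAP 4.7), so a child observed for two days weighs the same as one observed for 28.

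The SAP allows for such children: the shell for Table 14.1.1.2 lists an adverse event as a reason for discontinuing the trial, separately from discontinuing treatment.

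**Working it through.** The plan states no figure on this point, so the check is mainly a comparison of the two paths for a child who has received at least one dose.

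| | Stop study drug (3.4.2) | Leave the study (3.4.1) |
|---|---|---|
| Best-interest trigger | Judged by Investigator, Sponsor or medical monitor; no reason named | Judged by Investigator; for safety reasons |
| Force | Mandatory | Mandatory |
| Later visits | In-hospital assessments if still admitted, then Day 14 and Day 28 | One Withdrawal visit, no End of Study visit |
| New non-serious AEs (4.1.2) | Collected to Day 28 | Collected to the Withdrawal visit |
| New SAEs judged unrelated (4.1.4) | Collected to Day 28 | Collected to the Withdrawal visit |
| New SAEs judged related (4.1.4) | Reportable at any time | Reportable at any time |
| AEs and SAEs already recorded (4.1.3, 4.1.4) | Followed to outcome | Followed to outcome |

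The paths differ in the visits and in the two rows on new events. Those rows rest on one inference: because nothing is scheduled after the Withdrawal visit, it is the child's last visit for sections 4.1.2 and 4.1.4.

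Two other provisions might have filled the gap.

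- The telephone contact in section 3.4.1 is for families who miss scheduled visits. A withdrawn child has none left.
- The reporting of related SAEs after the last visit is narrow. Section 4.1.4 tells Investigators not to rely on being unable to rule out a causal link, and to ask whether study drug is the most likely cause.

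Days of new-AE collection lost = Day of End of Study visit − day of withdrawal.

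- At nominal Day 28: 28 − 1 = 27, 28 − 2 = 26 and 28 − 3 = 25 days for withdrawal on Day 1, 2 or 3.
- The ±2-day window puts the visit at Day 26 to Day 30. For Day 2 the loss is 26 − 2 = 24 to 30 − 2 = 28 days. Over Days 1 to 3 it is 26 − 3 = 23 to 30 − 1 = 29 days.

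Weight of one child in a cohort of 12 active and 3 placebo (section 3.6.1.3): 1/12 = 8.3% and 1/3 = 33.3%.

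**The case against.** A reader might infer that any safety concern forces a dosed child out of the study. The text does not say that. The Investigator must consider withdrawal itself to be in the child's interest, and the same sentence asks for every reasonable attempt at retention. Sections 3.4.1 and 3.4.2 can fairly be read as two decisions, one about participation and one about drug.

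The named reactions are also already protected. Severe or serious hypersensitivity, drug-induced acute respiratory distress and the need for ventilation or excess high-flow oxygen all lead to drug discontinuation with continued follow-up (3.3.7.2, 3.4.2, 3.6.3.8). So the documents do not support saying that follow-up is lost in the children most likely to have delayed reactions. Section 1.3.3 adds that AEs from treatment-emergent antibodies are not expected.

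Nor does all AE collection end that day, as the comparison shows. Section 4.1.4 gives delayed-onset events as its example of related SAEs reportable after the last visit.

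The mismatch with section 3.6.1.7 is softer than a flat contradiction. That section says should, the waiver of the End of Study visit is explicit, and the Schedule lets the Withdrawal visit share a column with the Day 14 visit. It is best described as an exception that 3.6.1.7 does not state.

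The 5.7% in section 1.2.3.2.2 invites the product 0.057 × 12 = 0.68 active children per cohort. But it counts children who stopped study drug in the first-in-infant study, which is the 3.4.2 event. It does not estimate study withdrawal.

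Finally, a child withdrawn because of a TEAE already counts in the row for at least one TEAE. That stands. Only later, different events could be missed, in the rows by preferred term, severity or seriousness.

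None of this supplies a rule for choosing between the sections or restores collection of new non-serious AEs and new unrelated SAEs.

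**Conclusion.** The point holds as a gap in follow-up and an unresolved overlap between sections. For a dosed child withdrawn for safety on Day 2, about 26 days of new-AE collection are lost (24 to 28 with the visit window), and that child is 8% of a cohort's active subjects or 33% of its placebo subjects. This assumes that the Withdrawal visit is the last visit and that a site takes the 3.4.1 path.

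How often that would happen is unknown, because the documents give no rate of safety-driven study withdrawal. A reader might infer that TEAE percentages are materially biased low; the documents do not support a size for any such bias. The analysis is descriptive, and SAP section 1 reports that only cohort 1 was filled, with 15 subjects randomized. The gap is still worth closing: it falls on the first objective and costs little to remove.

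**What to change.** Reconcile sections 3.4.1, 3.4.2, 3.6.1.6 and 3.6.1.7 and Schedule footnote e, so that a site can tell which path applies and 3.6.1.7 states any exception. This review takes no position on when a child should stop drug or leave the study.

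Whichever path is taken, add a data-collection rule. For any dosed child withdrawn for a reason other than withdrawn consent, loss to follow-up or death, record AE/SAE status at Day 14 and Day 28 by telephone or from the hospital record while consent stands. Extend the collection periods in 4.1.2 and 4.1.4 to match.

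Because enrolment has ended, the abbreviated report should show any study withdrawals separately from drug discontinuations, with days observed. At present the shell for Table 14.3.1.1 merges the two in one row, while SAP 6.1 describes that row as drug discontinuation only.

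The cost is a wording change and at most two contacts per affected child.

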3.4.2. DISCONTINUATION OF STUDY DRUG

A subject must be discontinued from study drug treatment if:

- The randomization code is broken prematurely by the Investigator or Sub-Investigator.
- A severe and/or serious hypersensitivity reaction to study drug occurs.
- A severe and/or serious acute respiratory distress reaction induced by study drug administration occurs.
- The subject needs to start treatment with one of the medications listed as prohibited (see section 3.3.7).
- The subject needs to start non-invasive respiratory support, invasive ventilation or HFOT at levels not enabling removal of the cannula for administration of the study drug nebulization and/or levels exceeding 2 L/kg/min. The event will be captured as an SAE and will be monitored until resolution, as described in section 4.1.4.

- If the Investigator or the Sponsor / medical monitor deems it is in the subject's best interest.
- If on Day 2 or Day 3, study drug initiation*** has not been successful after 60 minutes, study drug treatment should be discontinued (i.e., in case dose initiation was not successful on Day 2, then no dosing on Day 3 should be done).

A subject may be discontinued from study drug treatment if an SAE occurs (if considered necessary or appropriate by the Investigator).

For subjects remaining hospitalized after study drug treatment discontinuation, in-hospital post-treatment assessments will be performed in addition as specified in the [Schedule of Assessments](#). Subjects who discontinued treatment prematurely (for any reason) should also attend the FU and EOS visits.

If a subject is discontinued from the study drug, the study monitor and the Sponsor are to be informed immediately.

